13.0 Study Timelines*

13.1 Describe the anticipated duration needed to enroll all study subjects.

Response: Two years

13.2 Describe the duration of an individual subject's participation in the study. Include length of study visits, and overall study follow-up time.

Response: Participant will only have one study visit lasting from 30-60 minutes.

13.3 Describe the estimated duration for the investigators to complete this study (i.e. all data is collected and all analyses have been completed).

Response: Three years

14.0 Setting

14.1 Describe all facilities/sites where you will be conducting research procedures. Include a description of the security and privacy of the facilities (e.g. locked facility, limited access, privacy barriers). Facility, department, and type of room are relevant. Do not abbreviate facility names.

NOTE: Examples of acceptable response may be: "A classroom setting in the Department of Psychology equipped with a computer with relevant survey administration software," "The angiogram suite at Buffalo General Medical Center, a fully accredited tertiary care institution within New York State with badge access," or, "Community Center meeting hall."

Response:

The Obstetrics and Gynecology clinical suite at Conventus Office Building, 4th floor for data acquisition; and [name] laboratory at Sherman Hall, South Campus of the University at Buffalo for data analysis. The de-identified data will be shared through UB-Box.

14.2 For research conducted outside of UB and its affiliates, describe:

- *Site-specific regulations or customs affecting the research*
- *Local scientific and ethical review structure*

NOTE: This question is referring to UB affiliated research taking place outside UB, i.e. research conducted in the community, school-based research, international research, etc. It is not referring to multi-site research. UB affiliated institutions include Kaleida Health, ECMC, and Roswell Park Cancer Institute.

Response:

N/A: This study is not conducted outside of UB or its affiliates.

15.0 Community-Based Participatory Research

15.1 Describe involvement of the community in the design and conduct of the research.

NOTE: Community-Based Participatory Research (CBPR) is a collaborative approach to research that equitably involves all partners in the research process and recognizes the unique strengths that each brings. CBPR begins with a research topic of importance to the community, has the aim of combining knowledge with action and achieving social change to improve health outcomes and eliminate health disparities.

Response:

N/A: This study does not utilize CBPR.

15.2 Describe the composition and involvement of a community advisory board.

Response:

N/A: This study does not have a community advisory board.

16.4 Describe your process to ensure that all persons assisting with the research are adequately informed about the protocol, the research procedures, and their duties and functions.

Response:

The study team has regular meetings to discuss and design the research project. All investigators are CITI trained. Only the PI, [name], and the study coordinator, will have direct contact with the study patients.

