7.0 Local Number of Subjects

7.1 *Indicate the total number of subjects that will be enrolled or records that will be reviewed locally.*

Response: 60 (sixty)

7.2 *If applicable, indicate how many subjects you expect to screen to reach your target sample (i.e. your screen failure rate).*

Response: 100

7.3 *Justify the feasibility of recruiting the proposed number of eligible subjects within the anticipated recruitment period. For example, how many potential subjects do you have access to? What percentage of those potential subjects do you need to recruit?*

Response: The PI sees an average of 5 new patients per month diagnosed with vulvodynia and has many established patients who can be assessed when they come in for follow-up. For affected women, the goal would be to recruit close to 100% of them. The Ob/Gyn practice is an eight-person general Ob/Gyn practice that sees 50-70 women per week for routine gynecologic care. Only a small fraction of these women will need to be recruited.

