11.0 Recruitment Methods

N/A: This is a records review only, and subjects will not be recruited. NOTE: If you select this option, please make sure that all records review procedures and inclusion/exclusion screening are adequately described in other sections.

11.1 *Describe when, where, and how potential subjects will be recruited.*

NOTE: Recruitment refers to how you are identifying potential participants and introducing them to the study. Include specific methods you will use (e.g. searching charts for specific ICD code numbers, Research Participant Groups, posted advertisements, etc.).

Response: Women will be approached by the PI when they come to the clinical suite for evaluation of vulvar pain (subjects). Women will be approached by their own provider prior to routine annual exam to ask permission for the PI or study coordinator to discuss the study with them (controls). Some women will be called by the study coordinator in advance of their scheduled clinic visit and invited to participate in the study to save time on the day of the visit. The consent form will be discussed with them and then signed when they arrive for their clinic visit.

11.2 *Describe how you will protect the privacy interests of prospective subjects during the recruitment process.*

NOTE: Privacy refers to an individual's right to control access to him or herself.

Response: Women will be approached by telephone prior to their study visit or in private once they have been ushered into an exam room by clinical staff. If a patient agrees to consider recruitment, study staff will then explain the study and patient's participation in a private room.

11.3 Identify any materials that will be used to recruit subjects.

NOTE: Examples include scripts for telephone calls, in person announcements / presentations, email invitations.

 For advertisements, include the final copy of printed advertisements with your submission. When advertisements are taped for broadcast, attach the final audio/video tape. *NOTE: You may submit the wording of the advertisement prior to taping to ensure there will be no IRB-required revisions, provided the IRB also reviews and approves the final version.*

Response: N/A – we are using a direct recruitment method.

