12.0 Procedures Involved*

12.1 Provide a description of **all research procedures or activities** being performed and when they are performed once a subject is screened and determined to be eligible. Provide as much detail as possible.

NOTE: This should serve as a blueprint for your study and include enough detail so that another investigator could pick up your protocol and replicate the research. For studies that have multiple or complex visits or procedures, consider the addition of a schedule of events table in in your response.

Response:

All procedures will be performed on the same day as screening and consent and are expected to take 30-60 minutes. An annotated pain map of the vulva will be created based on subjective assessment of pain, and thermographic imaging.

- A. Images and Thermographic readings will be taken with an infrared camera prior to any physical contact with the vulva of the patient other than by placing a calibrated paper drape circumferentially on the vulva outside of the area of interest. The drape will be calibrated to maintain pain map/image size comparison between patients.
- B. Subjective pain at several predetermined loci will be assessed with a cotton swab (standard of care) and rated on a Likert scale of 0-10. This data will be added to the thermographic map.
- C. Comparative analysis of the two measures will be performed (separate from visit). Patient demographic and health data (see table below) will be collected by direct participant interview and review of the patient's chart in Allscripts.

12.2 Describe what data will be collected.

NOTE: For studies with multiple data collection points or long-term follow up, consider the addition of a schedule or table in your response.

Response:

Patient Name

DOB

MR#

Date of Visit

Vulvar images, both plain and infrared.

Pain sensitivity data on a Likert scale of 0-10 using cotton-tipped swabs.

Status (PWD or Control)

Race

Gravida

Para

Vaginal Births

Cesarean Births

Sexually Active

Dyspareunia

Smoking

Marital Status

Education Level

Medical History

Depression

Anxiety

Fibromyalgia

Chronic Pelvic Pain

Interstitial Cystitis

Endometriosis

Irritable Bowel Syndrome

TMJ

Other

h/o yeast infections

h/o BV

h/o abuse

PWD Patients Only

Symptom Duration

Pain Map Score

Pain Diary Score

FSDS

Previous Rx (Y/N)

Previous Rx (type)

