19.0 Data Management and Analysis*

19.1 *Describe the data analysis plan, including any statistical procedures. This section applies to both quantitative and qualitative analysis.*

Response: Both visible and infrared images will be acquired using our state-of-the-art FLIR E-95 camera. The E-95 is one of the best IR cameras available. It has very high spatial resolution and temperature sensitivity. In summation: if there is any correlation between temperature and vulvodynia, this camera will be able to see it. The camera's software stores both of these images along with metadata in a single jpeg. We have already designed our own custom software to extract the raw temperature data from these files. Our software will control the camera remotely through a USB link. This, along with mounting the camera on a tripod, will ensure that there is minimal "smearing" of the image due to small uncontrollable movements of the person operating the camera. This will give us the highest accuracy possible. In addition, our graphical software interface will allow the user to mark the image to indicate where sensitivity to pressure or an increase in thermal activity was observed. As we expect spatial variation in temperature from the affected area to the unaffected, we will provide the user with a variety of options for subtracting the average body temperature to make the difference more visible. All data will be stored securely to maintain patient confidentiality. Once we have collected enough data, we can begin the process of establishing the metrics by which we can diagnose the patients. Considering all of our data (pressure, temperature, color (from visible light image)) we can determine the connection of each to a positive diagnosis and assign a finally probability to our result.

19.2 *If applicable, provide a power analysis.*

NOTE: This may not apply to certain types of studies, including chart/records reviews, survey studies, or observational studies. This question is asked to elicit whether the investigator has an adequate sample size to achieve the study objectives and justify a conclusion.

Response: This is a pilot study. No power analysis will be performed.

19.3 *Describe any procedures that will be used for quality control of collected data.*

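### The endpoint is heat located at tender sites, but the plan has no masking to keep the thermal readings and swab ratings independent

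*Combined protocol and SAP*

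**What the plan says.** **Measurements.** Section 3.1 defines the endpoint as thermographic inflammation in the painful areas, cases against controls. Section 12.1 A states: "Images and Thermographic readings will be taken with an infrared camera prior to any physical contact with the vulva". Section 12.1 B then tests predetermined loci with a cotton swab, each rated 0 to 10, and says of the ratings: "This data will be added to the thermographic map". Section 12.1 C places the comparison of the two measures outside the visit.

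**Reading the images.** Under section 19.1, custom software extracts raw temperatures from the camera files. The same section says the interface will "allow the user to mark the image to indicate where sensitivity to pressure or an increase in thermal activity was observed", and it gives the user several ways to subtract average body temperature.

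**People.** Section 16.4 names a small team, including the principal investigator and the coordinator, who alone "will have direct contact with the study patients". Under section 11.1 the principal investigator approaches affected women when they attend for vulvar pain, while controls are first asked by their own provider. Section 7.3 adds: "The PI sees an average of 5 new patients per month diagnosed with vulvodynia". Group status is on the list of data to be collected (section 12.2).

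**Masking.** None is described, either of one measure to the other or of anyone to group. Sections 14.1 and 20.1 provide for de-identified or coded data.

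**The concern.** A co-location endpoint asks whether two measurements agree at the same site. If whoever takes one of them can see the other, part of the agreement may come from the measuring process. Three routes are open:

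- **Swab.** No force, order of loci or script is stated, and section 4.1 says the reproducibility of this examination has not been assessed. An examiner who has seen a warm spot could press or prompt differently there.
- **Marking.** A user who knows which loci are tender, or which group the woman is in, could more readily call those loci warm.
- **Subtraction.** With several options and no fixed rule, the one that makes a tender area stand out can be chosen after the fact.

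Each woman has one visit (section 13.2). Images can be re-read masked later, but swab ratings influenced by the image cannot be retaken. The same data are to supply diagnostic metrics (section 19.1) and a database for pattern finding (section 1.0), so built-in agreement would carry forward.

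**Working it through.** The plan gives no figure to reproduce: section 19.2 says no power analysis will be performed, and no correlation or agreement statistic is specified. The check is therefore a reading of the text, followed by illustrations whose bias inputs are all assumptions.

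**Reading**

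| Requirement for independence | What the plan states |
|---|---|
| Swab ratings taken without sight of the image | Image exists first (12.1 A); withholding not mentioned |
| Thermal reading made without ratings or group | Ratings added to the map (12.1 B); user marks either finding on the image (19.1); no masking |
| Fixed thermal rule | Several subtraction options, no threshold (19.1) |
| Group unknown to contact staff | Different recruitment routes (11.1), small contact team (16.4); swab operator not named |

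**Illustration 1: swab route.** Let temperature T be standardised normal and independent of pain. Suppose seeing the image raises the rating by delta at loci above the median temperature, and ratings otherwise have SD s.

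- Covariance of T and rating = delta x 1/sqrt(2 pi) = 0.399 delta.
- Rating variance = s^2 + 0.25 delta^2.
- r = 0.399 (delta/s) / sqrt(1 + 0.25 (delta/s)^2).

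Low end, delta 0.5 and s 3: delta/s = 0.167, so r = 0.0665 / 1.003 = 0.07. High end, delta 1.5 and s 2: delta/s = 0.75, so r = 0.299 / 1.068 = 0.28. The true correlation is zero in both.

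**Illustration 2: marking route, agreement within cases.** Assume heat and pain are independent, half of the loci are painful, and heat is marked at 30% of loci, plus b at painful ones. With b = 0.20, observed agreement is 0.5 x 0.50 + 0.5 x 0.70 = 0.60. Chance agreement is 0.50, so kappa = 0.10 / 0.50 = 0.20. A simulation (4,000 runs, 30 cases, t-test on the within-woman difference in marking rate between painful and non-painful loci, two-sided 0.05) gives these false-positive rates:

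| b | Expected kappa | 5 loci | 8 loci |
|---|---|---|---|
| 0 | 0 | 4.8% | 5.3% |
| 0.10 | 0.10 | 21% | 31% |
| 0.20 | 0.20 | 58% | 82% |
| 0.30 | 0.30 | 89% | 98.5% |

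The number of loci is also an assumption; section 12.1 says only that there are several.

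**Illustration 3: marking route, cases against controls.** Take 30 per group (section 1.0), the same true marking rate p0 of 10% to 30% in both, and an excess b in cases from expectation alone. The chance of a significant result is Phi((b - 1.96 SE0) / SE1), with SE0 the pooled and SE1 the unpooled standard error. For p0 = 0.10 and b = 0.20: SE0 = sqrt(2 x 0.2 x 0.8 / 30) = 0.1033 and SE1 = sqrt((0.09 + 0.21) / 30) = 0.100, giving 49%. Across p0, the chance is 12% to 19% for b = 0.10, 35% to 49% for 0.20 and 65% to 78% for 0.30, against a nominal 5%.

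**The case against.** The plan already contains real protections. Loci are predetermined, so the examiner cannot choose sites after seeing a warm spot. The woman gives the rating. Raw temperatures are extracted by software, the comparison is made away from the visit, and data are coded. These points stand and narrow the risk. They do not close it: pressure and prompting remain free, coding is not said to hide group or ratings, and no section makes raw temperatures, rather than user marks, the analysed variable.

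A reader might infer more than the text supports:

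- *That the swab examiner knows the group and has seen the image.* The operator is not named, the public text does not show sections 16.1 to 16.3, and no section says the image is viewed before or during the swab test. Group knowledge is probable; sight of the image is possible.
- *That taking the image first is a fault.* It keeps swab contact from altering temperature, and expectation during the swab test cannot change temperatures already stored.
- *That one person marks both findings.* Section 19.1 describes what the interface permits; it does not assign a reader.
- *That examiner bias at the swab step inflates a case-control difference in temperature.* It can affect which areas count as painful, but not the recorded temperatures.

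The bias inputs come from no document, and the low end of illustration 1 is negligible. The pilot label in section 19.2 explains the absent power analysis; it does not bear on masking.

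**Conclusion.** The concern holds as an absent safeguard. The documents do not show that bias will occur. Following the plan as written allows each measure to be taken or read with knowledge of the other, when the endpoint is that the two coincide. The exposed steps are swab pressure and prompting, manual marking of warm areas and the choice of subtraction; stored raw temperatures are not exposed.

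The size cannot be derived from the documents. Under the stated assumptions, the swab route alone produces a correlation of 0.07 to 0.28 from nothing. In the marking illustration, a 20-point excess at painful loci produces a kappa of about 0.2. The marking figures apply only if user marks, rather than raw temperatures, are analysed. This is a cheap improvement to make before enrolment.

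**What to change.** **Section 12.1.** Keep imaging before contact. State that the infrared image is not shown to the person applying the swab until all ratings are recorded, with the loci tested in a fixed order.

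**Section 19.1.** Have the existing analysis laboratory (section 14.1) extract raw temperatures at the predetermined loci from coded images, under one pre-set subtraction rule and without group or swab ratings. Lock these values before the overlay. Use them for the thermal-pain and case-control comparisons, in place of user marks made on an unmasked image.

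**Limitation to state.** This does not mask the examiner to group. That is largely unworkable, because cases attend for vulvar pain and controls have none.

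**Cost.** A change in working order and in who sees the display. The camera is already controlled remotely by the study's software and the laboratory is already separate. The examiner cannot review the infrared image during the swab test, and framing must be checked without showing it to the examiner. The plan does not say whether the software can hide the display, so that needs confirming.

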17.0 Other Approvals

17.1 Describe any approvals that will be obtained prior to commencing the research (e.g., school, external site, funding agency, laboratory, radiation safety, or biosafety).

Response:

N/A: This study does not require any other approvals.

18.0 Provisions to Protect the Privacy Interests of Subjects

18.1 Describe how you will protect subjects' privacy interests during the course of this research.

NOTE: Privacy refers to an individual's right to control access to him or herself. Privacy applies to the person. Confidentiality refers to how data collected about individuals for the research will be protected by the researcher from release. Confidentiality applies to the data.

Examples of appropriate responses include: "participant only meets with a study coordinator in a classroom setting where no one can overhear", or "the participant is reminded that they are free to refuse to answer any questions that they do not feel comfortable answering."

Response:

Participants will meet with the PI or the study coordinator in a private exam room in the clinical suite where no one can overhear. They will be given ample time to consider study participation, ask questions, and sign the consent. All patients will be reminded that participation is voluntary and will not affect the care they receive.

18.2 Indicate how the research team is permitted to access any sources of information about the subjects.

*NOTE: Examples of appropriate responses include: school permission for review of records, consent of the subject, HIPAA waiver. This question **does apply** to records reviews.*

Response:

Consent and HIPAA authorization will be obtained for access to the patient's medical record to confirm medical history and medications which may impact patient's participation.

19.0 Data Management and Analysis*

19.1 *Describe the data analysis plan, including any statistical procedures. This section applies to both quantitative and qualitative analysis.*

Response: Both visible and infrared images will be acquired using our state-of-the-art FLIR E-95 camera. The E-95 is one of the best IR cameras available. It has very high spatial resolution and temperature sensitivity. In summation: if there is any correlation between temperature and vulvodynia, this camera will be able to see it. The camera's software stores both of these images along with metadata in a single jpeg. We have already designed our own custom software to extract the raw temperature data from these files. Our software will control the camera remotely through a USB link. This, along with mounting the camera on a tripod, will ensure that there is minimal "smearing" of the image due to small uncontrollable movements of the person operating the camera. This will give us the highest accuracy possible. In addition, our graphical software interface will allow the user to mark the image to indicate where sensitivity to pressure or an increase in thermal activity was observed. As we expect spatial variation in temperature from the affected area to the unaffected, we will provide the user with a variety of options for subtracting the average body temperature to make the difference more visible. All data will be stored securely to maintain patient confidentiality. Once we have collected enough data, we can begin the process of establishing the metrics by which we can diagnose the patients. Considering all of our data (pressure, temperature, color (from visible light image)) we can determine the connection of each to a positive diagnosis and assign a finally probability to our result.

19.2 *If applicable, provide a power analysis.*

NOTE: This may not apply to certain types of studies, including chart/records reviews, survey studies, or observational studies. This question is asked to elicit whether the investigator has an adequate sample size to achieve the study objectives and justify a conclusion.

Response: This is a pilot study. No power analysis will be performed.

19.3 *Describe any procedures that will be used for quality control of collected data.*

Response: We are focusing on detecting vulvodynia alone, so we will choose patients that are otherwise healthy. Any patient with a pre-existing condition that may affect the outcome of our experiments will be excluded from the study.

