1.0 Study Summary

Study Title	Objective Assessment of Pain Thresholds in Women with Vulvodynia
Study Design	Clinical Trial
Primary Objective	Develop annotated pain maps showing region and size of area sensitive to mechanical stimulus. The pain maps will be created by combining IR images, photographs, and clinical input, and will be correlated with patient co-morbidities.
Secondary Objective(s)	a-Determine changes in the location and size of sensitive regions following various conventional clinical interventions for vulvodynia. b-Develop a large, information-rich database of annotated pain maps from patients, and use Artificial Intelligence to identify patterns and trends.
Research Intervention(s)/ Investigational Agent(s)	Infrared imaging of the vulva and assessment of pain intensity using cotton-tipped swab.
IND/IDE #	N/A
Study Population	Women with vulvodynia and healthy controls
Sample Size	60 women (30 in each group)
Study Duration for individual participants	One day 1 hour

Study Specific Abbreviations/ Definitions	
--	--

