2.0 Objectives*

2.1 *Describe the purpose, specific aims, or objectives of this research.*

Response:

We have been developing a novel medical technique for the diagnosis and classification of vulvodynia. The technique will quantitatively quantify the magnitude and location of areas of sensitivity to touch/pressure and simultaneously use thermal and photo imaging to identify regions of inflammation. The technique builds on current methodology used in assessment and knowledge about the known pathophysiology of the disorder. For this aspect of study, we will assess thermal indicators of inflammation with an infrared camera and subjective pain sensitivity with traditional methods. Through this combination of measurements, we plan to expand the diagnostic tools used in patient care as well as on the classification of this heterogeneous disorder. Specific aims include developing annotated pain maps that show regions of sensitivity and changes in temperature; determining changes in the above parameters during and after traditional medical treatment for the condition; and developing a large database of annotated pain maps for use with artificial intelligence to identify patterns and trends which will be correlated with clinical outcome data.

2.2 *State the hypotheses to be tested, if applicable.*

NOTE: A hypothesis is a specific, testable prediction about what you expect to happen in your study that corresponds with your above listed objectives.

Response:

Women with vulvodynia will show specific patterns of pain sensitivity and inflammatory changes (identified by thermography) compared to women without vulvar pain.

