3.0 Scientific Endpoints*

3.1 *Describe the scientific endpoint(s), the main result or occurrence under study.*

NOTE: Scientific endpoints are outcomes defined before the study begins to determine whether the objectives of the study have been met and to draw conclusions from the data. Include primary and secondary endpoints. Some example endpoints are: reduction of symptoms, improvement in quality of life, or survival. Your response should not be a date.

Response:

Thermographic evidence of inflammation in the areas of pain sensitivity in women with provoked vulvodynia compared to normal controls.

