22.0 Withdrawal of Subjects*

N/A: This study is not enrolling subjects. This section does not apply.

22.1 *Describe anticipated circumstances under which subjects may be withdrawn from the research without their consent.*

Response:

Participants who consent but cannot complete the study procedures, if for example they have abnormal findings at the time of the exam, will be withdrawn from the study at the time of the study visit.

22.2 *Describe any procedures for orderly termination.*

NOTE: Examples may include return of study drug, exit interview with clinician. Include whether additional follow up is recommended for safety reasons for physical or emotional health.

Response:

If patient cannot complete the study at the time of the study visit, no additional procedures will be performed at that time

22.3 *Describe procedures that will be followed when subjects withdraw from the research, including retention of already collected data, and partial withdrawal from procedures with continued data collection, as applicable.*

Response:

If a patient chooses to return to complete the study procedures, her biographical and demographic data will be saved. If she cannot return, previously collected data will be destroyed for control participants and saved for affected women, since this data would be collected for the routine assessment anyway. If a participant decides to leave the research, she can contact the investigator so that the investigator can remove any personal medical information from the study records.

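### Section 19.1 says the camera will see any correlation between temperature and vulvodynia, but that ability depends on between-woman variation and 30 women per group, so a null result could be misread as no link

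*Combined protocol and SAP*

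**What the plan says.** Section 19.1 asks for the data analysis plan and any statistical procedures. The answer opens with the infrared camera, of which it says "It has very high spatial resolution and temperature sensitivity". It sums up that "if there is any correlation between temperature and vulvodynia, this camera will be able to see it", then moves to file format, remote control and tripod mounting. It gives no figure for the camera's sensitivity and none for variation between women. It names no test, alpha, SD, effect size or confidence interval.

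Section 19.2 then says: "This is a pilot study. No power analysis will be performed".

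The quantity of interest is a comparison between groups. Section 3.1 gives the endpoint as "Thermographic evidence of inflammation in the areas of pain sensitivity in women with provoked vulvodynia compared to normal controls". The hypothesis in section 2.2 is also comparative: "Women with vulvodynia will show specific patterns of pain sensitivity and inflammatory changes (identified by thermography) compared to women without vulvar pain". The Study Summary sets 60 women, 30 in each group, and section 7.1 agrees on 60. Section 13.2 adds that "Participant will only have one study visit lasting from 30-60 minutes", so each woman has a single imaging occasion.

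**The concern.** A correlation between temperature and a disease is a property of a set of women, some affected and some not. It cannot be seen in one image, however good the camera. A very sensitive camera can make measurement error small. It cannot reduce the natural spread of vulvar temperature from woman to woman, and it cannot add women. Those two things fix how small a group difference the study can detect.

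The sentence therefore moves from a property of the instrument (small temperature differences can be measured) to a property of the study (any association will be found). It is the plan's only affirmative statement about detection, and it stands where a reader looks for the statistical basis of the conclusions.

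The reading of a null result is at stake. If any correlation would be seen, then not seeing one implies there is none. Nothing elsewhere in the plan blocks that inference, because there is no commitment to interval estimates and no statement of what a null result would mean.

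**Working it through.** **No figure to reproduce.** The number 60 is given without derivation, so the check asks what 30 v 30 can do under stated assumptions.

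**Inputs from the documents**
- 30 women per group (Study Summary); 60 in total (section 7.1).
- A between-group comparison (sections 2.2 and 3.1).
- One visit per woman (section 13.2), hence one imaging occasion each.

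**Assumptions, because the documents are silent**
- One temperature summary per woman, compared by a two-sample t-test at two-sided 5%.
- Differences expressed in units of the between-woman SD, since no SD in degrees is given.
- All 30 per group evaluable, with 25 and 20 as a range. No dropout rate is stated. Section 22.3 says that, for women who cannot return to complete the procedures, "previously collected data will be destroyed for control participants and saved for affected women", so the evaluable number could fall below 30.

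**Precision.** The standard error of the difference is SD × √(2/30) = 0.258 SD. The 95% CI half-width is t(0.975, 58) × 0.258 = 2.002 × 0.258 = 0.52 SD. An observed difference of exactly zero would still be compatible with about half an SD in either direction.

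**Smallest difference with 80% power.** The normal approximation gives (1.960 + 0.842) × √(2/n). The noncentral t calculation is slightly larger and is the one used in the conclusion.

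| Evaluable per group | Normal approximation | t-test |
|---|---|---|
| 30 | 0.72 SD | 0.74 SD |
| 25 | 0.79 SD | 0.81 SD |
| 20 | 0.89 SD | 0.91 SD |

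**Power at fixed true differences, 30 v 30, t-test**

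| True difference | Power | Chance of missing it |
|---|---|---|
| 0.2 SD | 12% | 88% |
| 0.3 SD | 21% | 79% |
| 0.5 SD | 48% | 52% |
| 0.8 SD | 86% | 14% |

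**What would be needed.** By the t-test, 80% power at 0.5 SD takes 64 per group. At 0.3 SD the solution is 175.4, so 176 per group.

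**The same result as a correlation.** With two equal groups, a difference d corresponds to a correlation of about d/√(d² + 4). For d = 0.74 this is 0.74/√(0.5476 + 4) = 0.35. This is the 0.74 SD threshold on another scale, not further evidence. No such correlation exists within the affected women alone, because diagnosis does not vary among them.

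**Sensitivity to the choice of test.** A one-sided 5% test lowers the 80% threshold for 30 v 30 to 0.64 SD (normal approximation). That is still far from any correlation.

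**The case against.** The strongest reply is that the sentence is about the camera. Its grammatical subject is the instrument, the text around it describes the equipment, and its opening words close that description. This stands: it is an exaggerated statement about an instrument, not a power claim for 30 v 30. Even so, what the camera is said to see is an association with a diagnosis, which no camera can deliver alone.

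A second reply is that section 19.2 calls the study a pilot and declines a power analysis, and that the template's own note allows this for some kinds of study. Section 19.1 also speaks of setting diagnostic metrics only once enough data are in hand, which is exploratory language. This stands too. The absence of a power calculation is no fault here, and the pilot label tells a careful reader not to treat a null as final. But it makes the unqualified sentence harder to justify: the plan does not assess what it can detect, yet says that nothing will be missed.

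A reader might infer that the investigators intend to report a null as proof of no link. The documents do not support that. They contain no rule for reading a null result, so the most that can be said is that one could be misread.

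Finally, a t-test on one summary per woman does not describe every analysis in view. Section 19.1 foresees contrasts between affected and unaffected areas within a woman, and section 12.1 has several pain loci per woman. The figures above apply to the between-group comparison that the endpoint and hypothesis name. They do not apply to within-woman contrasts, or to the relation of temperature to pain score.

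**Conclusion.** The point holds in a limited form. Camera sensitivity does not give this study the ability to see any correlation between temperature and vulvodynia. With 30 per group, a true difference of 0.5 SD would be missed about half the time and one of 0.3 SD about four times in five. Only differences of about 0.74 SD or more would be found with 80% power, or about 0.81 to 0.91 SD if 25 to 20 per group are evaluable.

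These figures rest on the assumed test, the assumed 5% two-sided level and standardised effects. They cannot be turned into degrees, because the plan defines no temperature summary and gives no SD. The qualitative conclusion does not depend on those choices, since no sample of this size detects every association.

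The sample size and the pilot status need not change. What needs correcting is the sentence, together with the lack of any statement on how a null result would be reported.

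**What to change.** In section 19.1:

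1. Limit the sentence to the instrument, for example that the camera can resolve small temperature differences within an image, with its stated sensitivity if available.
2. Add the precision of the design as an assumption-based figure: under a two-sample t-test at two-sided 5% with 30 evaluable per group, the 95% CI half-width is about 0.52 SD and 80% power is reached only from about 0.74 SD. Give the range for 25 and 20 evaluable per group.
3. Commit to reporting the between-group temperature difference as an estimate with a 95% CI. For the interval to be in degrees, the temperature summary taken from each woman must be named.
4. State that a null result is inconclusive for differences inside that interval.

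The cost is one paragraph. No more participants, visits or measurements are needed. The downside is that the stated claim becomes less favourable: the plan would acknowledge that moderate differences may be missed.
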